 - ALT or AST $>$ 3 x ULN and Total Bilirubin \geq 2 x ULN and ALP $<$ 2 x ULN
 - ALT or AST $>$ 5 x ULN and \leq 8 x ULN persistent for more than 2 weeks

- ALT or AST > 8 x ULN
- Lack of efficacy: during the core phase treatment period, patients with GH level > 2.5ug/L and/or IGF-1 > ULN (age and sex related) be discontinued from the study unless clinical benefit has been observed as per the investigator's judgment.

Patients who withdraw prematurely from the core phase cannot participate in the extension phase.

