10.1 Analysis sets

10.1.1 Full Analysis Set

The Full Analysis Set (FAS) comprises all patients to whom study treatment has been assigned by randomization. According to the intent to treat principle, patients will be analyzed according to the study treatment they have been assigned to during the randomization procedure.

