10.5 Secondary objectives

All secondary efficacy endpoints will be based on the FAS. All secondary endpoints measured up to 3 months of study treatment will be summarized by dose level at randomization study treatment and total-group. All secondary endpoints measured after 3 months of study treatment will be summarized by total-group only.

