4.1.10 Evaluation time window

GH and IGF-1 measurements taken within 35 days after the date of LAR injection are allowed and the last values of 5-point mean GH and IGF-1 within window will be used as the value of the corresponding month. For assessments beyond 3 months of study treatment, the ongoing patients will be counted in the denominator of calculation of response rate, if they have reached at each visit (e.g. Assessments collected at end of the study treatment of Core Phase will be treated at those at 12 months of study treatment as long as those were collected within the time window specified in the above). Discontinued patients are included in the denominator of calculation of response rate in the core phase and are included at a visit to which a patient reached in the extension phase.

MRI collected within +/- 35 days from the date of visit is allowed. For corresponding visit, the patient will be counted at a specific visit if they have reached at each visit.

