5.1 General presentation of descriptive summaries

Categorical data (e.g. gender, race, etc.) will be summarized by frequency count and percentages. Percentages will be calculated using the number of patients in the relevant population or subgroup as the denominator.

Continuous data (e.g. age, body weight, etc.) will be summarized by appropriate descriptive statistics (i.e. mean, standard deviation, median, minimum and maximum).

Data through 24 months of study treatment and at end of study treatment will be summarized except for study disposition, drug administration record and adverse events/serious adverse events. For study disposition, drug administration record and adverse events/serious adverse events, all data even beyond 24 months of study treatment will be summarized and listed.

All data will be listed appropriately.

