5.9.2 Secondary analyses

The FAS will be used for the following analyses.

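### SAP 4.1.10 changes the response-rate denominator between Month 12 and Month 18, so the by-visit rates are not on one base and no rate over all FAS patients is planned for the extension

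*SAP*

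**What the plan says.** **Analysis set.** Protocol 10.5 states: "All secondary efficacy endpoints will be based on the FAS". Protocol 10.1.1 defines that set as one that "comprises all patients to whom study treatment has been assigned by randomization". SAP 5.9.2 repeats the choice for the secondary analyses: "The FAS will be used for the following analyses". SAP 5.1 adds: "Percentages will be calculated using the number of patients in the relevant population or subgroup as the denominator".

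**Denominator rule.** SAP 4.1.10 is more specific. For the core phase: "Discontinued patients are included in the denominator of calculation of response rate in the core phase". Read to its end, the same sentence counts them "in the core phase and are included at a visit to which a patient reached in the extension phase", so in the extension they count only at visits they reached. Ongoing patients after Month 3 are likewise counted once they reach a visit.

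**Who can reach Month 18 or 24.** Protocol 7.1.3.1: "Patients who withdraw prematurely from the core phase cannot participate in the extension phase". Protocol 4.1 enrols Month 12 responders in the extension and lets the others in if the investigator expects them to benefit.

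**Display.** Protocol 10.5.2.2 asks for total-group proportions with exact 95% intervals at Months 18 and 24. SAP 5.9.2.2 updates the response rates and bar charts by visit, with subgroups by prior somatostatin analogue treatment.

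**The concern.** A reader who sees response rates by visit, headed FAS, will read them as one series. They are not one series. A patient who leaves in the core phase weighs on the Month 6 to 12 percentages and then disappears from those at Months 18 and 24. A patient who leaves during the extension drops out at the next visit. The percentage can rise between Month 12 and Month 18 with no patient changing response status, and the rise could be taken as a late gain or as proof of durability.

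The patients removed are unlikely to be a random subset, because some of the stopping and entry rules depend on GH and IGF-1. Neither document plans a rate on one common denominator across the two phases.

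**Working it through.** **1. Which rule governs.** The FAS statements name a set of patients; SAP 4.1.10 says who is counted at each visit. I take the specific rule as governing. By the Month 12 report every patient had either reached each core visit or discontinued, so the core denominator is the 33 randomised patients (SAP 2), assuming none is excluded for missing consent (SAP Table 4-1). At Months 18 and 24 it is n, the number who reached the visit.

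**2. How far n depends on response.**
- Protocol 6.3.1, core phase: uncontrolled patients on 20 or 40 mg have the dose raised at Month 3 and Month 7. Patients on 60 mg are stopped at Month 3, 6 or 9 only if both markers fail and the investigator sees no benefit.
- Protocol 7.1.3.1 is broader. Its item begins "Lack of efficacy: during the core phase treatment period, patients with GH level" and goes on to cover failure on GH and/or IGF-1 at any dose, again unless benefit is seen.
- Protocol 6.3.1, after Month 12: patients on 60 mg failing both markers leave unless benefit is seen.
- Protocol 6.1.5 makes the extension optional. Table 7-1 footnote D puts the first extension visit on the day of the Month 12 sample, which goes to a central laboratory (7.2.1.1, 7.2.1.2). Selection on the Month 12 value itself may therefore be weak.

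Selection on response is real but partial.

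**3. Size.** The plan gives no figure for Months 18 or 24, so there is none to reproduce. Let R be the responders at Month 12, L those who later lose response, and assume no late gains.
- Month 12 rate = R/33.
- Printed extension rate = (R − L)/n. With L = 0 this is the Month 12 rate times 33/n.
- The printed rate stays at or above R/33 if and only if L/R ≤ 1 − n/33.

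Assumed inputs:
- R = 10, from 33 × 0.314 = 10.4 (the 12-month rate in the medication-naive trial, Protocol 1.2.1.2).
- R = 6, from 33 × 0.173 = 5.7 (the 3-month crossover rate, Protocol 10.8).
- n = 30, from 33 × 0.9 = 29.7. The plan's 10% drop-out was set for the Month 3 endpoint, so it does not establish retention at Month 24.
- n = 25 and n = 20 have no source and serve only to show the range.

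| Denominator | 33/n | R = 10, none lost | R = 10, one lost | R = 6, none lost | R = 6, one lost |
|---|---|---|---|---|---|
| 33 (all FAS) | 1.00 | 30.3% | 27.3% | 18.2% | 15.2% |
| n = 30 | 1.10 | 33.3% | 30.0% | 20.0% | 16.7% |
| n = 25 | 1.32 | 40.0% | 36.0% | 24.0% | 20.0% |
| n = 20 | 1.65 | 50.0% | 45.0% | 30.0% | 25.0% |

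The bound 1 − n/33 is 9% at n = 30, 24% at n = 25 and 39% at n = 20. At n = 30 it is less than one patient for either R, so a single loss takes the printed rate below Month 12 (30.0% against 30.3%; 16.7% against 18.2%). At n = 25 with R = 10, two responders can be lost and 8/25 = 32.0% is printed, against 8/33 = 24.2% of the FAS.

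**4. Precision.** Exact 95% intervals: 10/33, 15.6% to 48.7%; 8/25, 14.9% to 53.5%; 8/33, 11.1% to 42.3%. They overlap widely.

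**The case against.** The rule is stated openly. The Month 18 and 24 endpoints belong to separate long-term objectives, for which describing the patients still on treatment is reasonable. No analysis compares Month 12 with Month 24. SAP 5.1 already gives counts with percentages, SAP 5.3 gives disposition by phase, and SAP 5.9.2.2 gives individual GH and IGF-1 plots. An all-FAS rate has a bias of its own, because it counts as failures those who left once the drug was marketed or who declined an optional extension. It would also be specified after the Month 12 results were known.

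Most of this stands, and it is why the prespecified rates should stay. What remains is that the displays put two denominators in one series, and that a reader would have to work out the common-denominator rate alone.

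A reader might infer four stronger points that the documents do not support:
- **That uncontrolled core patients as a class are removed.** Protocol 6.3.1 raises the dose of those on 20 or 40 mg. The broader item in 7.1.3.1 also allows for clinical benefit.
- **That core withdrawals are non-responders at Months 6 to 12 by a written rule.** SAP 4.1.9 states non-response for Month 3 only. For later core visits it is implied by the place these patients keep in the denominator.
- **That the printed rate will rise while responders are lost.** At n = 30 one loss lowers it; the effect needs poorer retention, which the documents do not show.
- **That SAP 4.1.10 contradicts the FAS.** An analysis set and a visit denominator are different things. The fault is a label that invites misreading.

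**Conclusion.** The point holds as a minor one. The denominator changes between Month 12 and Month 18, the remaining group is partly selected on response, and no common-denominator rate is planned. The likely direction is upward. The size is unknown because the documents give no retention counts: 2 to 3 percentage points at n = 30, and about 10 points at n = 25 with R = 10, both under assumed inputs and no change in response. Only descriptive secondary extension endpoints are affected, and no test depends on them.

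**What to change.** In SAP 5.9.2.2:

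1. Keep the prespecified rates. Print n/N at each visit in the rate tables and on the bar charts, and footnote that the denominator changes after Month 12.
2. Add supplementary Month 18 and Month 24 total-group rates over all FAS patients, counting those who did not enter, left or have missing values as non-responders, with exact 95% intervals. Label them as a lower bound added after the Month 12 report, and footnote how many left because the drug became commercially available.
3. Optionally, tabulate Month 18/24 response by Month 12 response. This answers a new question about maintenance, which the plan does not pose. Its cells would be small: 8/10, for example, has a 95% interval of 44% to 98%.

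The cost is labels, a footnote and one extra row per rate table, all from GH and IGF-1 already collected, with no protocol change. The drawback is that the all-FAS rate treats leavers for commercial supply as failures, so it should be read beside the prespecified rate and should not replace it.

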4.2 Data included in the analyses

The first interpretable result (FIR) was generated when the last patient completed 3 months assessment with data cut-off on 31-Jul-2014. Primary CSR, which contained results of primary and key secondary analyses, was generated when the last patient completed the 12 months assessment with data cut-off on 2-Apr-2015.

The final analysis will be performed after all patients discontinued the study or study drug has been available on the market, and cumulative data will be reported in a final CSR. For the final analysis, only data through 24 months of study treatment and data at end of study treatment visit will be summarized, except for study disposition and adverse events/serious adverse events, as only minimal data will be collected beyond 24 months of study treatment. Study disposition and adverse events/serious adverse events data beyond 24 months will be summarized in addition to listings.

For efficacy endpoints, all primary and key secondary analyses were already reported in 12 month CSR. Updates of other secondary endpoints will be provided in the final CSR.

If an event continues until the end, then the event will be considered continuing and not having documented end date. This approach applies, in particular, to adverse event and concomitant medication reports. For these events, the end date will not be imputed and therefore will not appear in the listings.

If it is required to impute an end date to be able to perform a specific analysis, (e.g. end date after the cut-off date) the data cut-off date will be imputed as the end date (to allow for calculation of treatment exposure duration for instance).

4.3 Analysis sets

Full analysis set (FAS) comprises of all patients to whom study treatment has been assigned by randomization. According to the intent to treat principle, patients will be analyzed according to the study treatment they have been assigned to during the randomization procedure.

Safety set includes all patients who received at least one dose of study treatment. Patients will be analyzed according to the study treatment according to the treatment they first received.

The rules for patient classification in the analysis sets (FAS and safety) are described hereafter:

T. I. I	D . 41 4 1
Table 4-1	Patient classification rule
I adic T-I	i alieni ciassincation rule

Analysis set	Protocol deviations that cause patients to be excluded from analysis and corresponding deviation codes from VAP Module 3
FAS	No written informed consent prior to any procedure (deviation code = I01)
Safety set	No written informed consent prior to any procedure (deviation code = I01)

The per-protocol set (PPS) and pharmacokinetic analysis set (PAS) discussed on the study protocol, will not be used for the final analysis since there is no pharmacokinetic analysis nor PPS analysis performed and all of them were already reported in [the 12 month CSR].

Although there is no PPS involved, all protocol deviations will be finalized before database lock and reported in the listing.

Analyses of efficacy endpoints will be based on the FAS. Safety analyses will be performed based on the safety set.

5 Statistical methods used in reporting

5.1 General presentation of descriptive summaries

Categorical data (e.g. gender, race, etc.) will be summarized by frequency count and percentages. Percentages will be calculated using the number of patients in the relevant population or subgroup as the denominator.

Continuous data (e.g. age, body weight, etc.) will be summarized by appropriate descriptive statistics (i.e. mean, standard deviation, median, minimum and maximum).

Data through 24 months of study treatment and at end of study treatment will be summarized except for study disposition, drug administration record and adverse events/serious adverse events. For study disposition, drug administration record and adverse events/serious adverse events, all data even beyond 24 months of study treatment will be summarized and listed.

All data will be listed appropriately.

5.2 Protocol deviation summaries

The number and percentage of patients in the FAS with any protocol deviation will be tabulated by the deviation category (as specified in the VAP Module 3).

5.3 Patient disposition

The FAS will be used for the following analyses.

Number of patients who are randomized and treated will be presented.

Number of patients who are still on-treatment, complete and discontinue at core phase will be presented. Primary reason for discontinuation at core phase will be summarized.

Number of patients who are still on-treatment, complete and discontinue at extension phase will be presented. Primary reason for discontinuation at extension phase will be summarized.

Number of patients who are beyond 24 months of study treatment and discontinue will be presented. Primary reason for discontinuation at extension phase will be summarized.

5.4 Demographics

Summary of demographics characteristics were reported in [the 12 months CSR] and not applicable in this document.

5.5 Medical history and current medical conditions

Due to few data changes since data cut-off for the analysis of [the 12months CSR], relevant medical history and current medical conditions will be summarized again by primary system organ class, preferred term, randomized dose level and overall for the FAS, although these were reported previously in [the 12 months CSR].

5.6 Prior therapies

Summaries of prior radiotherapy and surgery were reported in [the 12 months CSR] and not applicable in this document.

Due to few data changes since data cut-off for the analysis of [the 12months CSR], prior medication will be summarized again by WHO drug reference list, randomized dose level and overall for the FAS, although these were reported previously in [the 12 months CSR].

5.7 Study medication

The following analyses will be conducted by study phase for the safety set.

The durations of exposure to the study drug and the number of injections received will be summarized. Duration of exposure is calculated as

Duration of exposure = min (last date of study drug + 27, date of death) – first date of study drug + 1

Number of patients with dose reduction and dose increase will be presented.

5.8 Concomitant therapy

Concomitant medications and significant non-drug therapies prior to and after the start of the study drug will be summarized by ATC class, preferred term, phase and overall for the safety set.

5.9 Efficacy evaluation

5.9.1 Primary analysis

Primary variable

The primary variable is the total-group response rate defined as the proportion of patients with the reduction of mean GH levels to $< 2.5 \mu g/L$ and the normalization of IGF-1 at 3 months of study treatment. This has already been reported in [the 12 month CSR].

Please see the Section 4.1.9 about how to handle missing values and discontinuations.

Primary analysis

The total-group response rate at 3 months of study treatment along with the corresponding Clopper-Pearson exact two-sided 90% confidence interval was reported in [the 12 months CSR] and not applicable in this document.

5.9.2 Secondary analyses

The FAS will be used for the following analyses.

5.9.2.1 Key secondary analyses

The response rate for patients with the reduction of mean GH levels to $< 2.5 \mu g/L$ and the normalization of IGF-1 at 3 months of study treatment along with the corresponding exact 95% confidence interval as well as respective response rate with mean GH and IGF-1 were reported in [the 12 months CSR] and not applicable in this document.

5.9.2.2 Other secondary analyses

Other secondary analyses for core phase

Most secondary objectives were reported in [the 12 months CSR] and not applicable in this document. The below analyses, which were previously performed, will be repeated with updated data for the final analysis (most likely at 18 months and 24 months of study treatment).

Proportions of overall patients with the reduction of mean GH levels to < 2.5 ug/L and normalization of IGF-1 will be updated along with subgroup analysis of SSA uncontrolled status, while SSA uncontrolled population is defined as patients who were pre-treated with SSA for >= 12 weeks and patients who were pre-treated with SSA for < 12 weeks or were not pre-treated with SSA are considered as others. Proportions of patients with the reduction of mean GH level to < 2.5 ug/L by visit and with normalization of IGF-1 by visit will be updated along with subgroup analysis of SSA uncontrolled status, respectively.

Bar charts for all total group response rate, proportion of patients with reduction of mean GH level to < 2.5 ug/L and proportion of patients with normalization of IGF-1 will be repeated by visit for updated data.

Total group response rate with over responder by visit will be also updated where over responder is defined as a patient with reduction of mean GH levels to <2.5 ug/L and IGF-1 reached lower than lower limit normal. This summary will be updated with SSA uncontrolled status subgroups as well.

Changes from baseline in mean GH and in normalization of IGF-1 will be updated by visit and SSA uncontrolled status, respectively, in addition to change from baseline in ring size and PRL.

Plots of individual patient absolute value of mean GH and IGF-1 will be re-ran as well.

Changes of tumor volume at 6 and 12 months of study treatment from baseline were reported in [the 12 month CSR] and not applicable in this document. The summary will be repeated by subgroup of categorical longest diameter with 10 mm cut-off in the final analysis. Changes and percent changes will be plotted along with the longest diameter as well.

5.10 Safety evaluation

For all safety analyses, the safety set will be used. All analysis through Month 3 was reported in [the 12 month CSR] and not applicable in this document.

The overall observation period will be divided into three mutually exclusive segments:

- 1. Pre-study treatment period: from day of patient's informed consent to the day before the first dose of study medication
- 2. On-study treatment period: from the day of first dose of study medication to 56 days after last dose of study medication
- 3. Post-study treatment period: starting at 57 days after last dose of study medication

5.10.1 Adverse events (AEs)

AEs will be coded using the Medical Dictionary for Regulatory Activities (MedDRA) terminology. The last version at the time of database lock will be used.

AEs will be graded according to the Common Terminology Criteria for Adverse Events (CTCAE) version 3.0. If CTCAE grading does not exist for an adverse event, grades 1-4 corresponding to the severity of mild, moderate, severe, and life-threatening will be used. CTCAE grade 5 (death) will not be used in this study; rather this information will be collected on the "Study phase completion – core study", "Study phase completion – extension study" or "Study completion" eCRF pages.

Summary tables for AEs have to include only AEs that started or worsened during the onstudy treatment period, the study treatment-emergent AEs. However, all AE data (including those from the pre and post-study treatment periods) will be listed and those collected during the pre and post-study treatment are to be flagged. Serious AEs, AEs leading to study drug discontinuation, AEs requiring dose adjustment or interruption and death will be listed.

Grouping of adverse events of special interest

Specific groupings of adverse events of special interest will be considered and the number of patients with at least one event in each grouping will be reported. Such groups consist of adverse events for which there is a specific clinical interest in connection with SOM230 treatment (i.e. where SOM230 may influence a common mechanism of action responsible for triggering them) or adverse events which are similar in nature (although not identical) within project defined group. The specific groupings of AEs as defined in the latest documentation available prior to database lock

will be used.

AE summaries using all available data

The following AE summaries will be provided by phase (core/extension) using all data up to data cut-off:

- AEs, regardless of study drug relationship, by primary system organ class and preferred term
- AEs, regardless of study drug relationship, by preferred term
- AEs suspected to be related to the study drug by primary system organ class and preferred term
- AEs, regardless of study drug relationship, by primary system organ class, preferred term and maximum CTCAE grade
- AEs suspected to be related to the study drug by primary system organ class, preferred term and maximum CTCAE grade
- On-treatment deaths by primary system organ class and preferred term
- Serious AEs (SAEs), regardless of study drug relationship, by primary system organ class, preferred term and maximum CTCAE grade
- AEs leading to study discontinuation, regardless of study drug relationship, by primary system organ class, preferred term and CTCAE grade
- AEs requiring dose adjustment or study drug interruption, regardless of study drug relationship, by primary system organ class, preferred term and maximum CTCAE grade
- AEs requiring significant additional therapy, regardless of study drug relationship, by primary system organ class, preferred term and maximum CTCAE grade
- AEs of special interest, regardless of study drug relationship, by category and preferred term
- AEs of special interest suspected to be related to the study drug by category and preferred term
- AEs of special interest leading to study discontinuation, regardless of study drug relationship, by category and preferred term

Study disclosure

For the legal requirements of ClinicalTrials.gov, two required tables on on-treatment adverse events which are not serious adverse events and on on-treatment serious adverse events and SAE suspected to be related to study treatment will be provided by system organ class and preferred term on the safety set population.

If for a same patient, several consecutive AEs (irrespective of study treatment causality, seriousness and severity) occurred with the same SOC and PT:

- a single occurrence will be counted if there is ≤ 1 day gap between the end date of the preceding AE and the start date of the consecutive AE
- more than one occurrence will be counted if there is > 1 day gap between the end date of the preceding AE and the start date of the consecutive AE

For occurrence, the presence of at least one SAE / SAE suspected to be related to study treatment / non SAE has to be checked in a block e.g., among AE's in a \leq 1 day gap block, if at least one SAE is occurring, then one occurrence is calculated for that SAE.

The number of deaths resulting from SAEs suspected to be related to study treatment and SAEs irrespective of study treatment relationship will be provided by SOC and PT.

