| 
A. pasireotide LAR injection and study visits every 28 days +/- 2 days.
 
B Patients' GH nadir within 2 hours after an oral glucose load with 75 g of glucose (OGTT) will be measured. The scheduled time points are at t0, oral glucose, t30, t60, t90, t120 (except for diabetic patients).
 
C Blood sampling of IGF-1 for PD assessment combines with efficacy assessment.
 
D For patients accepting to continue in the extension phase, at 12 months, a 13th injection of the same study treatment received in the core phase will be administered. Patients continuing the study treatment with pasireotide LAR in the extension phase will have the option of receiving pasireotide therapy as long as they do not fulfill any of the study discontinuation criteria or until pasireotide LAR is commercially available or until the pasireotide LAR development program is discontinued (whichever comes first).
 
Visit 21 and Visit 777 are on the same day for patients willing to continue in the extension phase.
 | | | | | | | | | | | | | | | | | | | | | |

[figure not shown]
[figure not shown]

Table 7-2 Extension Visit evaluation schedule

| | Category | Reference | | | | | | | | | | | | | | | | End of study treatment for Ext | Study completion |
|--|----------|------------|-----|-----|-----|-----|-----|-----|-----|-----|-----|-----|-----|-----|-----|-------------------------|-----|---------------------------------|------------------|
| Visit number | | | 21 | 22 | 23 | 24 | 25 | 26 | 27 | 28 | 29 | 30 | 31 | 32 | 33 | 34 and following visits | 778 | 779 | |
| Study day | | | 337 | 365 | 393 | 421 | 449 | 477 | 505 | 533 | 561 | 589 | 617 | 645 | 673 | 701, 729, 757, 813... | | 56 days following the last dose | |
| Month (1 month = 28 days) | | | 12 | 13 | 14 | 15 | 16 | 17 | 18 | 19 | 20 | 21 | 22 | 23 | 24 | 25- | | | |
| pasireotide LAR Injection ^A | D | 6.1 | 13 | 14 | 15 | 16 | 17 | 18 | 19 | 20 | 21 | 22 | 23 | 24 | 25 | 26- | | | |
| Physical Examination | S | 7.2.2.1 | | X | X | X | X | X | X | X | X | X | X | X | X | | X | X | |
| Vital signs | D | 7.2.2.2 | | X | X | X | X | X | X | X | X | X | X | X | X | | X | X | |
| Weight | D | 7.2.2.3 | | X | X | X | X | X | X | X | X | X | X | X | X | | X | X | |
| ECG | D | 7.2.2.5.1 | | | | X | | | X | | | X | | | X | | X | X | |
| Gallbladder ultrasound | D | 7.2.2.4.10 | | | | X | | | X | | | X | | | X | | X | | |
| Hematology | D | 7.2.2.4.1 | | | | X | | | X | | | X | | | X | | X | X | |

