7.1.3 End of treatment visit including study completion and premature withdrawal

Patients who discontinue study treatment before visit 777 (if patient is in the core phase of the study) or visit 33 (if patient is in the extension phase of the study), should be scheduled for a visit as soon as possible, at which time all of the assessments listed for the visit 777 / 778 will be performed ([Table 7-1](#) and [Table 7-2](#)). An End of Treatment eCRF page should be completed, giving the date and reason for stopping the study treatment.

At a minimum, all patients who discontinue study treatment, including those who refuse to return for a final visit, will be contacted for safety evaluations (visit 779) during 56 days following the last dose of study treatment.

Patients who discontinue study treatment should be considered withdrawn from the study after the final visit assessments are performed or when it is clear that the patient will not return for these assessments.

If a study withdrawal occurs, or if the patient fails to return for visits, the investigator must determine the primary reason for a patient's premature withdrawal from the study and record this information on the End of Treatment eCRF page. The investigator must inform the premature withdrawal to Novartis.

For criteria for premature withdrawal refer to [Section 7.1.3.1](#).

End of treatment visit and Study completion visit for patients treated for more than 2 years (after Visit 33)

If a patient discontinues after 2 years of treatment (after Visit 33), only the assessments with an asterisk in [Table 7-2](#) need to be performed on visit 778 and visit 779.

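### Extension-phase AE percentages pool Months 12-24, with scheduled laboratory and ECG testing, and an open-ended later period without it; the key tables should be split at Month 24

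*SAP*

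**What the plan says.** **Grouping.** SAP 5.10.1 introduces its list of AE tables with "The following AE summaries will be provided by phase (core/extension) using all data up to data cut-off". Thirteen summaries follow, and core/extension is the only time split. SAP 5.1 bases percentages on numbers of patients.

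**Length of the extension.** Under footnote D of protocol Table 7-1, patients who continue "will have the option of receiving pasireotide therapy as long as they do not fulfill any of the study discontinuation criteria", or until marketing or the end of the development programme. Protocol 4.1 and SAP section 2 also set no fixed end.

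**Testing after Month 24.** In Table 7-2 the column for Visit 34 and later shows the injection and a pregnancy test, with AEs and comments collected continuously. Protocol 7.1.3 adds: "If a patient discontinues after 2 years of treatment (after Visit 33), only the assessments with an asterisk in" Table 7-2 are needed at the end visits. The asterisked items are study completion data, AEs and comments.

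**Treatment of later data.** SAP 4.2 restricts most summaries to 24 months plus the end-of-treatment visit, "as only minimal data will be collected beyond 24 months of study treatment". AEs are exempt: "adverse events/serious adverse events data beyond 24 months will be summarized in addition to listings". SAP 5.1 repeats the exemption for disposition, "drug administration record and adverse events/serious adverse events, all data even beyond 24 months of study treatment will be summarized and listed".

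**What is separated at Month 24.** Disposition is: "Number of patients who are beyond 24 months of study treatment and discontinue will be presented" (SAP 5.3). Exposure is not: "The following analyses will be conducted by study phase for the safety set" (SAP 5.7).

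**The concern.** An abnormal laboratory value or ECG has to be measured before it can be recorded as an AE. When scheduled testing stops, AEs found mainly by testing (hyperglycemia, liver events and QT prolongation are the clearest examples) are likely to be picked up less completely, while time at risk keeps accumulating and differs between patients. One percentage over both periods cannot show which of the two forces produced it.

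Safety in the extension phase and safety of long-term treatment are both stated objectives (protocol Table 3-1, SAP Table 3-1). The extension AE tables are the natural place to look for an answer, and the planned layout makes their percentages hard to read as long-term risk.

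**Working it through.** The plan states no figure to reproduce here. The check sets the visit schedule against the table plan.

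**Step 1. Scheduled tests in the two parts of the extension (protocol Table 7-2, 7.1.3).** Visits 22 to 33 are Months 13 to 24, which is 33 - 22 + 1 = 12 visits. The quarterly tests fall at Months 15, 18, 21 and 24, which is 4 occasions.

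| Test | Visits 22-33 | Visit 34 onward | End visits if stopping after Visit 33 |
|---|---|---|---|
| Fasting glucose | 12 | 0 | 0 |
| ECG | 4 | 0 | 0 |
| Liver tests | 4 | 0 | 0 |
| HbA1c | 4 | 0 | 0 |
| Pregnancy test | 12 | kept | not asterisked |

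**Step 2. Where the SAP cuts the data.**

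| Output | Data beyond Month 24 | Shown separately after Month 24 |
|---|---|---|
| Laboratory, liver, ECG (4.2, 5.1) | not summarised, except end-of-treatment visit | not needed |
| Disposition (5.3, Table 8-1 item 1) | summarised | yes |
| Exposure, injections (5.1, 5.7) | summarised | no, by phase only |
| AEs, 13 tables (4.2, 5.1, 5.10.1) | summarised | no, by phase only |

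The subheadings in SAP 5.10.2 and 5.10.3 speak of all available data. I read them as subject to the limit in 4.2 and 5.1.

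**Step 3. What the pooled percentage measures.** For one AE row, let p be the proportion of extension patients with the AE recorded through Month 24. Among the rest, let q be the proportion with a first record after Month 24. Then

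pooled percentage = p + (1 - p) × q.

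Let Q be the value q would have had if scheduled testing had continued. If extra testing can only add detections, 0 ≤ q ≤ Q, so

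p ≤ pooled percentage ≤ p + (1 - p) × Q.

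The pooled figure is therefore at or above the Months 12-24 percentage and at or below what continued testing would have shown. Its position between these limits depends on how long patients stayed on drug after Month 24 and on how much detection fell. The documents give neither, so no size can be computed.

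**Step 4. Can a reader separate the periods?** The AE listings show study day (SAP 4.1.4, 5.10.1), so a split by hand is possible. No planned table gives AEs or patient-time after Month 24. This is inferred from the two-level phase grouping and from Table 8-1, which adds a beyond-24-month item for disposition only; table shells are not part of the documents.

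**The case against.** The strongest defence is that the SAP already protects the most direct measures. Laboratory shift tables, glucose and HbA1c summaries, liver thresholds and QT tables rest on the tested period, apart from end-of-treatment values. This stands, and it limits the point to the AE tables.

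Second, protocol 8.1.1 counts an abnormal test as an AE only if it is symptomatic, clinically significant, or needs therapy or a change of study drug. Many test-only findings would be AEs in neither period. This also stands and reduces the likely effect.

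Third, protocol 6.1.5 describes the extension as 12 more months, so later AEs might not belong to it. That reading fails. Protocol 4.1, Table 7-1 footnote D and SAP section 2 make the extension open-ended. If it did end at Month 24, the later AEs that SAP 4.2 promises to summarise would have no place in the phase tables.

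Fourth, a Month 24 split does not make the extension comparable with the core. Ascertainment already falls at Month 12: Table 7-1 schedules 14 post-dose ECGs (Visits 5, 6, 9, 11, 12-20 and 777) and 14 sets of liver tests (Visits 5, 6, 8, 9, 12-20 and 777), against 4 of each in Months 12-24. Extension patients are also selected. This stands. The split separates the two extension regimes and does no more than that.

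A reader might go further and infer that safety monitoring ends at Month 24. The documents do not support this. AEs are sought by questioning at each visit (protocol 8.1.1), blood glucose monitoring is required during treatment (inclusion criterion 4, protocol 6.3.3.1), and unscheduled tests remain possible. What ends is scheduled detection.

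**Conclusion.** The point holds for the AE tables of SAP 5.10.1. Each extension percentage combines a period with scheduled testing and an open-ended one without it, although the SAP itself treats Month 24 as the point after which data become minimal.

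The size is unknown. It would be tempting to conclude that the extension tables understate long-term risk, or to attach a number. Neither is supported: longer follow-up pushes the percentage up, reduced detection pushes it down, and the documents give no patient numbers, follow-up times or detection rates after Month 24.

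The conclusion assumes that no Month 24 split is hidden in unseen table shells and that some test-detected AEs would be missed without scheduled tests. Safety is descriptive, no formal comparison of phases is planned, and efficacy is unaffected. Severity is minor: a cheap improvement to reporting.

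**What to change.** In SAP 5.10.1, present at least two extension summaries separately for data through Month 24 and beyond Month 24: all AEs by system organ class and preferred term, and AEs of special interest by category and preferred term. Show the number of patients and the patient-time on drug in each period. Footnote that scheduled laboratory and ECG testing stopped after Month 24.

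Confine any exposure-adjusted rate to the core and Months 12-24, or give it the same caveat if it is shown after Month 24, because reduced detection still affects that rate.

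The cost is a few extra tables built from AE onset and dosing dates already collected. Cells will be sparse, with at most 33 patients. If they are judged too sparse to tabulate, the footnote with patient-time per period gives most of the benefit. No protocol change is needed.
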